PHYSICAL EXERCISE GUIDED BY ACTIVE VIDEO GAMES FOR OPTIMIZING
CLINICAL AND PSYCHOSOCIAL OUTCOMES IN OLDER ADULTS WITH KNEE
AND/OR HIP OSTEOARTHRITIS UNDER A COMMUNITY-BASED
REHABILITATION MODEL.

Date: November 28th, 2022

Study documents

1. GENERAL INFORMATION.

- **Unique Protocol ID:** UNAB-FCR-KINE2023B
- **Brief Title:** Active Video Games for Older Adults With Knee and/or Hip Osteoarthritis.
- **Official Title:** Physical Exercise Guided by Active Video Games for Optimizing Clinical and Psychosocial Outcomes in Older Adults With Knee and/or Hip Osteoarthritis Under a Community-based Rehabilitation Model.
- **Study Type:** Interventional
- **Number of Arms:** 2

2. SCIENTIFIC BACKGROUND.

Osteoarthritis (OA) is highly prevalent, and its incidence increases with aging populations (1). OA is characterized by articular cartilage degeneration, stiffness, inflammation, and musculoskeletal pain (2). In addition, the associated deterioration of health-related quality of life may influence therapeutic adherence and progression to future joint replacement (3,4). It appears that symptoms rather than structural impairment determine the risk of falling in older people with OA (5), so pain, loss of strength, and postural balance are underlying mechanisms for both falls and the clinical picture of OA itself (6). Moreover, the psychosocial sequelae are often underestimated because OA and pain are usually considered benign and unavoidable consequences of aging (7).

Physical exercise in people with knee and hip OA improves clinical aspects and psychosocial aspects such as self-efficacy, social function, and reduction of depression and isolation, among others (8,9). Adherence to exercise is fundamental and is closely related to user satisfaction (10,11). There are several barriers to physical exercise by older adults, such as lack of social support, transportation problems, and prioritization of basic needs; however, a determining factor is lack of motivation (12). In this regard, a study indicates that in Latin America, lack of motivation is among the main reasons for abandoning physical exercise (13).

The technological development of the last decades has allowed the incorporation of virtual reality into the healthcare field, favoring user motivation (14,15). Virtual reality is an experience based on the interactive digital simulation of environments and objects (14,16). These systems are categorized as non-immersive, semi-immersive, and immersive. Non-immersive systems use monitors or television screens, semi-immersive

systems use panoramic screens to enhance the immersive experience, and immersive systems use head-mounted displays or multi-projected environments that generate a strong sense of immersion (17). It has been posited that the cost and expertise required to operate immersive systems may hinder their widespread use in clinical settings (18). In addition, the immersive sensation could produce symptoms such as visual fatigue and dizziness (cybersickness). On the other hand, non-immersive systems using commercially available home consoles are now considered an attractive and more accessible alternative to more sophisticated immersive systems (19,20).

Unlike traditional video games that use a standard command or joystick, active video games (AVGs) (also called exergames) use motion monitoring systems such as accelerometers, gyroscopes, haptic technology, and video capture (16). AVGs have been defined as a "combination of video game technologies and exercise routines to motivate physical activity among individuals or groups," recognizing that exercise in older people requires a greater understanding of the complexity of interaction with computer systems (21).

Conventional physical rehabilitation (CPR) consists of traditional physical exercises that improve functional capacity (22,23). Over the past few years, it has been suggested that incorporating AVGs into CPR can optimize clinical and psychosocial outcomes in the elderly (24-26). AVGs have been reported to promote improvements in functional mobility, coordination, muscle strength, and cognitive function in older people (27-29). In addition, AVGs improve walking ability (30) and postural balance (31), as well as social well-being (perception of loneliness, social connectedness, and positive attitudes) (24). However, this research has focused on healthy elderly (30-33) and patients with neurocognitive pathologies (29,34-37). On the other hand, little information is available on older people with musculoskeletal conditions such as OA (38-40). In this regard, a systematic review conducted in patients with knee and/or hip OA indicates that the evidence is insufficient and inconclusive regarding the effectiveness of AVGs (38). Moreover, one study concludes that AVGs are a feasible and acceptable intervention for patients with knee OA (39). Interestingly, both studies raise the benefits and potential of AVGs in this population, urging further clinical trials (38,39).

3. RESEARCH QUESTION AND HYPOTHESIS.

- **Research question:** In older adults with knee and/or hip OA. Is AVG-guided physical exercise adjunct to CPR more effective than CPR alone in improving clinical and psychosocial outcomes?
- **Working hypothesis:** In older adults with knee and/or hip OA, AVG-guided physical exercise adjunct to CPR is more effective than CPR alone in improving clinical and psychosocial outcomes.

4. OBJECTIVES.

General objective: To determine the effects of an AVG-guided physical exercise program adjunct to CPR on clinical and psychosocial outcomes in older adults with knee and/or hip OA attended at a community-based family health center.

Specific objectives:

1. To characterize the study sample from sociodemographic, anthropometric, clinical, and psychosocial perspectives.
2. To compare the results of the primary outcome (functional mobility) and secondary outcomes between the study groups (experimental and control) in the different instances of outcome measurement.
3. To evaluate the clinical significance of the interventions and the clinical relevance of the interventions as perceived by the participants.

5. METHODS.

Study design and setting.

The design is a two-arm parallel randomized clinical trial (RCT) and will be conducted according to the CONSORT statement. A control group (CG) will perform CPR, and an experimental group (EG) will perform AVG adjunct to CPR. Subjects will be invited to participate upon admission to the rehabilitation unit of a family health center. All study requirements will be explained, and all subjects will be required to sign an informed consent form.

Sample calculation.

The a priori calculated sample size using G*Power yielded 50 subjects. Statistical power $(1-\beta)=0.8$ and significance $(\alpha)=0.05$ were considered. In addition, a moderate effect size $(ES)=0.51$ was considered for the TUG test (functional mobility) to

detect a minimum clinically important difference (MCID) of 1.4 seconds. Ten subjects will be added for a potential dropout of 20%, finally estimating a sample of 60 subjects (CG=30; EG=30).

Participation criteria.

- Inclusion criteria: Age ≥ 60 and ≤ 84 years; Diagnosis of mild or moderate OA of the knee and/or hip; Independent walking capacity of at least 15 meters
- Exclusion criteria: Inability to interact with active video games; Undergoing treatment with opioids or other medications with a potential influence on the outcomes of interest; < 13 points in the abbreviated version of the Mini-Mental State Examination (MMSE-EFAM); OA associated with infectious, autoimmune, fractures or surgery; Participate or have participated in another physical-cognitive rehabilitation program during the last 3 months.

Randomization and allocation concealment.

A stratified randomization will be applied to balance the two study groups according to "age" (60-69, 70-79, 80-84 years) and "sex" (male, female). Allocation concealment will be ensured through sealed and consecutively numbered opaque envelopes.

Sample characterization.

Sociodemographic (age, sex, and education) and clinical characteristics (diagnosis of OA, comorbidity, history of falls, technical aids, and pharmacotherapy) will be collected by interview. In addition, height, body weight, and body mass index will be measured.

Study outcomes.

An experienced physical rehabilitation professional will perform the measurements in a blinded manner.

a) Primary outcome measure:

- Functional mobility. Timed Up and Go (TUG). Number of seconds required to get up from seated position, walk 3 m, turn, and return to seated position on chair. Time Frame: Five-time points. Baseline (pre-intervention); at week 4 (after ten sessions from baseline); at week 7 (after 20 sessions from baseline); and week 10 (after 30 sessions from baseline). In addition, four weeks after the completion of the intervention.

b) Secondary outcome measures:

- Lower body strength: 30-s chair stand. Number of full stands in 30 s with arms folded across chest. Time Frame: Five-time points. Baseline (pre-intervention); at week 4 (after ten sessions from baseline); at week 7 (after 20 sessions from baseline); and week 10 (after 30 sessions from baseline). In addition, four weeks after the completion of the intervention.
- Upper body strength. 30-s arm curl. Number of bicep curls in 30 s holding hand weight (women 5 lb; men 8 lb). Time Frame: Five-time points. Baseline (pre-intervention); at week 4 (after ten sessions from baseline); at week 7 (after 20 sessions from baseline); and week 10 (after 30 sessions from baseline). In addition, four weeks after the completion of the intervention.
- Aerobic endurance. 2-min step test. Number of full steps completed in 2 min, raising each knee to point midway between patella and iliac crest (score is number of times right knee reaches target). Time Frame: Five-time points. Baseline (pre-intervention); at week 4 (after ten sessions from baseline); at week 7 (after 20 sessions from baseline); and week 10 (after 30 sessions from baseline). In addition, four weeks after the completion of the intervention.
- Lower body flexibility. Chair sit-and-reach. From sitting position at front of chair, with leg extended and hands reaching toward toes, number of inches (+or –) from extended fingers to tip of toe. Time Frame: Five-time points. Baseline (pre-intervention); at week 4 (after ten sessions from baseline); at week 7 (after 20 sessions from baseline); and week 10 (after 30 sessions from baseline). In addition, four weeks after the completion of the intervention.
- Upper body flexibility. Back scratch. With one hand reaching over shoulder and one up middle of back, number of inches between extended middle fingers (+ or –). Time Frame: Five-time points. Baseline (pre-intervention); at week 4 (after ten sessions from baseline); at week 7 (after 20 sessions from baseline); and week 10 (after 30 sessions from baseline). In addition, four weeks after the completion of the intervention.
- Hand grip strength. Number of kg measured with a Jamar dynamometer. Time Frame: Five-time points. Baseline (pre-intervention); at week 4 (after ten sessions from baseline); at week 7 (after 20 sessions from baseline); and week 10 (after 30 sessions from baseline). In addition, four weeks after the completion of the intervention.

- Functional disability. Western Ontario McMaster Osteoarthritis Index (WOMAC) questionnaire. Score obtained on the scale of items grouped into 3 dimensions: pain, stiffness, and difficulty in performing tasks. Scores range from 0 to 96, where 0 represents the best health status and 96 the worst possible status. Time Frame: Five-time points. Baseline (pre-intervention); at week 4 (after ten sessions from baseline); at week 7 (after 20 sessions from baseline); and week 10 (after 30 sessions from baseline). In addition, four weeks after the completion of the intervention.
- Cognitive performance. Montreal Cognitive Assessment (MoCA) test. Score obtained in the development of the tests. It considers executive functions, attention, abstraction, memory, language, viso-constructive abilities, calculation, and orientation. MoCA scores range from 0 to 30; higher scores indicate a better cognitive performance. Time Frame: Three-time points. Baseline (pre-intervention); and week 10 (after 30 sessions from baseline). In addition, four weeks after the completion of the intervention.
- Pain intensity. Visual Analog Scale (VAS). 100 mm straight line with two labels ("no pain" and "worst possible pain") at each end. Time Frame: Five-time points. Baseline (pre-intervention); at week 4 (after ten sessions from baseline); at week 7 (after 20 sessions from baseline); and week 10 (after 30 sessions from baseline). In addition, four weeks after the completion of the intervention.
- Pressure pain threshold. Wagner® FPX-25 algometer. It is expressed in kilogram/cm². Time Frame: Five-time points. Baseline (pre-intervention); at week 4 (after ten sessions from baseline); at week 7 (after 20 sessions from baseline); and week 10 (after 30 sessions from baseline). In addition, four weeks after the completion of the intervention.
- Health-related quality of life. SF-12v2 Chile-Spanish Questionnaire. Score from 0-100 points. Assessment of 8 dimensions (physical functioning [PF], role-physical [RP], bodily pain [BP], general health [GH], vitality [VT], social functioning [SF], role-emotional [RE], and mental health [MH]), and two summary scores (physical component summary [PCS] and mental component summary [MCS]). Time Frame: Three-time points. Baseline (pre-intervention); and week 10 (after 30 sessions from baseline). In addition, four weeks after the completion of the intervention.
- Adherence to treatment. Number of effective assistances at the end of treatment. A participant with an attendance $\geq 2/3$ of the total (30 sessions) is considered "adherent"

(≥ 20 sessions). Time Frame: One-time point. At week 10 (after 30 sessions from baseline).

- User satisfaction. The average score of 3 questions (overall level of satisfaction, expectation fulfillment, and recommendations to others) using a scale of 1 to 7 points, where 1 is the worst evaluation, and 7 is the best evaluation. Time Frame: Three-time points. At week 4 (after ten sessions from baseline); at week 7 (after 20 sessions from baseline); and week 10 (after 30 sessions from baseline).
- Therapeutic alliance. Subscale of the Pain Rehabilitation Expectations Scale (PRES). The score ranges from 1 to 44; a higher score is a higher therapeutic alliance. Time Frame: Three-time points. At week 4 (after ten sessions from baseline); at week 7 (after 20 sessions from baseline); and week 10 (after 30 sessions from baseline).

Interventions.

Two experienced physiotherapists will perform the interventions. For both groups, the duration will be ten weeks with a frequency of 3 sessions per week (30 sessions). The intensity of the interventions in both groups will be controlled using a scale of 0 to 10 points, adjusting individually as "light" (effort < 5) and "moderate" (effort 5 to 6). For the progression of intensity, it is considered: i) Session 1 to 10 "light" 70% and "moderate" 30% of the session time; ii) Session 11 to 20 "light" 50% and "moderate" 50% of the session time; iii) Session 21 to 30 "light" 30% and "moderate" 70% of the session time. Adverse events, medications, and general health status will be monitored throughout the experimental period. The interventions are described below:

- Control Group (CG): Will receive a routine of four blocks of conventional exercises (50 minutes per session): Aerobic, muscle strengthening, postural balance, and flexibility. A warm-up phase will be performed before the exercise routine and a cool-down phase after the routine. In addition, before and after the session, physical agents will be applied in a standardized manner (electrotherapy and thermotherapy).
- Experimental group (EG): Will perform the same procedures as the CG, although the conventional exercise routine will last 30 minutes. Then, this group will perform an AVG intervention for 20 minutes so that the exercise time will be the same in both groups (50 minutes per session). The week before the interventions start, this group's participants will have a familiarization session with the AVGs. The AVG routine will be performed using a set of selected exercises and dynamic activities from the "Ring fit adventure" video game available for the Nintendo Switch® console.

REFERENCES.

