The description of quantitative indicators (continuous or discrete) will be done using measures of central tendency (mean or median) and dispersion (standard deviation, interquartile ranges, and confidence intervals) according to their normality distribution. For the description of categorical variables (nominal and ordinal), absolute and relative frequency measures will be used. The R v.4.1.2 software will be used for the analyses ($p < 0.05$). The assumptions of normality and homoscedasticity will be verified using the Shapiro-Wilk and Levene tests, respectively. For variables that do not meet the assumption of normality, a two-step rank transformation will be applied. A two-way, repeated measures ANOVA will be used to determine intragroup and intergroup differences. Model effects are Group, Time, and their interaction over time (Group \times Time). Tukey's post hoc test will be used for variables with Group \times Time interaction. The statistical analyst will be blinded for the intervention groups, and in addition, an intention-to-treat analysis (multiple imputation method) will be considered for handling potential incomplete data. Clinical significance (ES) of interventions will be determined using Cohen's "d" (< 0.2 =negligible, $0.2-0.49$ =small, $0.5-0.79$ =moderate; ≥ 0.8 =large). Additionally, at the end of the intervention, patients will be asked to rate their overall change in clinical status (pain and functionality) using a 15-point scale. The global rating of change ranges from +7 ("a very great deal better") to 0 ("about the same") to -7 ("a very great deal worse"). The interpretation of changes is: 1-3 points=small, 4-5=moderate, and 6-7=large.

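### The dropout allowance leaves 48 participants, not the calculated 50, and the stated 80% power depends on settings that the plan does not report

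*Combined protocol and SAP*

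**What the plan says.** The sample-size paragraph (protocol section 5, Sample calculation) reports: "The a priori calculated sample size using G*Power yielded 50 subjects". Its inputs are power 0.8, significance 0.05 and an effect size of 0.51, described as moderate, for TUG. The stated aim is to "detect a minimum clinically important difference (MCID) of 1.4 seconds". The allowance for loss follows: "Ten subjects will be added for a potential dropout of 20" per cent, which gives 60 participants, 30 per arm.

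TUG is measured at five time points: baseline, weeks 4, 7 and 10, and a last visit described as "In addition, four weeks after the completion of the intervention" (section 5, Primary outcome measure).

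The SAP names the analysis: "A two-way, repeated measures ANOVA will be used to determine intragroup and intergroup differences". Its effects are Group, Time and Group × Time, with Tukey comparisons where the interaction is present. It also plans an intention-to-treat analysis with multiple imputation. The only scale the documents attach to the abbreviation ES is in the SAP: "Clinical significance (ES) of interventions will be determined using" Cohen's d, where 0.5 to 0.79 counts as moderate.

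The paragraph does not give the G*Power test, the effect-size metric, the SD, the number of measurements, the between-visit correlation, or the course of the 1.4 s difference over the visits.

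**The concern.** Two things do not fit together. First, the allowance is meant to protect the calculated 50 against a 20% loss, but it was computed as 20% of 50 and not as the number to enrol so that 80% of it equals 50. If dropout is as expected, the trial ends below its own target.

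Second, the plan attaches 80% power to a clinically important difference on the primary outcome without any condition. In a five-visit repeated measures analysis, power for a given difference in seconds depends strongly on how closely a participant's TUG times correlate across visits, and on when the difference appears. Without these, a reader faced with a non-significant TUG result cannot judge how much it says about a 1.4 s effect.

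**Working it through.** **Inputs from the documents.** Power 0.80, alpha 0.05, effect size 0.51, difference 1.4 s, N = 50, ten added, 20% dropout, 1:1 allocation, m = 5 visits.

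**Inputs assumed.** 0.51 is Cohen's d on raw TUG scores. Then SD = 1.4/0.51 = 2.745 s (SD² = 7.536) and, for two groups, f = 0.51/2 = 0.255. The correlation ρ is the same for every pair of visits, and no sphericity correction is applied.

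**1. Reproducing 50.** One Group × Time convention uses λ = f²(N − 2)(m − 1), with (m − 1) and (N − 2)(m − 1) degrees of freedom. At N = 50, λ = 0.065025 × 48 × 4 = 12.48 on 4 and 192 df, and power is 80.9%. It is 79.9% at N = 49. The smallest N reaching 80% is therefore 50, which is the plan's figure. This setting fits the five visits and the SAP's model, but the match is an inference about what was run.

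**2. The dropout allowance.**
- 50 + 10 = 60.
- 60 × 0.80 = 48, or 24 per arm.
- Losing ten of 60 is 10/60 = 16.7%, so 60 protects the 50 only up to that rate.
- Keeping 50 after a 20% loss would take 50/0.80 = 62.5, that is, 63.

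**3. Power at 48, same convention.** λ = 0.065025 × 46 × 4 = 11.96 on 4 and 184 df. Power is 78.9%, two percentage points below the value at 50.

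**4. The condition behind the 80%.** For a specified group difference at each visit, λ = (n/2) × SS / [SD²(1 − ρ)] with n per arm. SS is the sum of squared deviations of the five differences from their mean; the df are 4 and 4(2n − 2). Three ways of reaching 1.4 s by week 10 and holding it at follow-up:

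| Difference by visit (s) | SS | ρ needed for 80% at 25 per arm |
|---|---|---|
| 0, 0.56, 0.98, 1.4, 1.4 (linear in weeks) | 1.427 | 0.807 |
| 0, 0.47, 0.93, 1.4, 1.4 (equal thirds) | 1.481 | 0.799 |
| 0, 1.4, 1.4, 1.4, 1.4 (immediate) | 1.568 | 0.787 |

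The calculation in step 1 takes no correlation as input but still implies one: its λ of 12.48 equals that of these profiles at ρ = 0.810, 0.803 and 0.792.

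**5. Sensitivity of power to ρ, sustained effect.** Worked example, immediate profile, ρ = 0.8. At 25 per arm, λ = 12.5 × 1.568/(7.536 × 0.2) = 13.0 and power is 82.7%. At 24 per arm, λ = 12 × 1.568/(7.536 × 0.2) = 12.5 and power is 80.9%. Ranges run from the linear to the immediate profile:

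| ρ | 25 per arm | 24 per arm |
|---|---|---|
| 0.5 | 37–40% | 35–39% |
| 0.7 | 59–63% | 57–61% |
| 0.8 | 78–83% | 77–81% |
| 0.9 | 98–99% | 98–99% |

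A simulation of 10,000 runs at 25 per arm and ρ = 0.8 gave 78.0% (linear) and 83.0% (immediate), against 78.5% and 82.7% from the formula.

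**The case against.** The strongest reply is that 50 is not wrong. It comes out exactly under a setting that agrees with the visit schedule and the SAP, so the missing inputs are a gap in reporting. That stands. A reader might infer from the missing inputs that 50 is an arithmetic error, perhaps because a single-visit two-group comparison with d = 0.51 would need 124 in total. The documents do not support this, since that comparison is not the planned test.

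A reader might also infer from the lower rows of the sensitivity table that the trial is underpowered. This is not supported either. The documents give no TUG correlation, and at 0.9 a sustained effect would almost always be detected. The grid rests on assumptions and belongs in the plan only if labelled so.

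The SAP does not say which effect was powered. With f = 0.255 and five visits, a calculation for the Group effect gives 46 at correlation 0.2 and 56 at 0.3, so it also brackets 50. This is a fair caution against treating the Group × Time route as established, and a further reason to name the test.

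On dropout, multiple imputation means that the analysis is not confined to 48 completers, and visits made before withdrawal still contribute. Analysis of 24 complete cases per arm is therefore one scenario. But imputation does not restore information that was never observed, and the sentence about the extra ten is itself offered as the cover for that loss. Adding 20% of the target is a common shortcut and the shortfall is two people, so the point is small. The arithmetic still does not deliver what the sentence implies.

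**Conclusion.** The dropout sentence is wrong as written: 20% loss from 60 leaves 48, not 50. This needs no assumption. The cost in power is about two percentage points (80.9% to 78.9%) under the one convention tested that returns exactly 50.

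The unconditional 80% for a 1.4 s difference is not supported by what the plan reports. It requires a between-visit correlation of about 0.79 to 0.81 at 25 per arm. That holds if 0.51 is d on raw scores, the SD is about 2.75 s, the correlation is constant, no sphericity correction is needed, the powered effect is Group × Time, and the difference is sustained to follow-up. If 0.51 was standardised differently, for example on change scores, the condition takes another form, which is why the metric has to be stated. None of this shows that true power is below 80%.

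**What to change.** Rewrite the sample-size paragraph and keep enrolment at 60.

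1. State that a 20% dropout leaves 48 evaluable participants (24 per arm), and give the power at 48. Under the inferred setting this is 78.9%; the sponsor should replace it with the value from the calculation actually run.
2. State the G*Power test, the effect-size metric, the number of measurements and the correlation that gave 50, and present the 80% as conditional on them.
3. Add one line of sensitivity, labelled as assumption. For example: for a sustained 1.4 s difference at 24 per arm, with SD 2.75 s, power is about 35–39% at correlation 0.5, 57–61% at 0.7, 77–81% at 0.8 and 98–99% at 0.9.

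The cost is one reworded paragraph and a slightly less favourable stated power. No participants, visits or analyses are added.

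### The 20% dropout allowance is taken on the 50 required, not the 60 enrolled: at 20% dropout, 60 leaves 48 completers, two short of the plan's own 50 (minor effect)

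*Combined protocol and SAP*

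**What the plan says.** The protocol's Methods section, under Sample calculation, gives the base number: "The a priori calculated sample size using G*Power yielded 50 subjects". It states power of 0.8, alpha of 0.05, and an effect size of 0.51 on the Timed Up and Go (TUG), tied to a difference of 1.4 seconds. It does not name the test or say whether it is one- or two-sided. The allowance for losses follows: "Ten subjects will be added for a potential dropout of 20%, finally estimating a sample of 60 subjects (CG=30; EG=30". Nothing elsewhere in the protocol or SAP defines the dropout rate differently or revises the 60.

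Two other places bear on what a dropout costs. TUG, the primary outcome, is measured at five time points (Study outcomes, primary outcome measure). On missing data, the SAP says that "an intention-to-treat analysis (multiple imputation method) will be considered for handling potential incomplete data". The planned analysis is a repeated measures ANOVA with Group, Time and their interaction.

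**The concern.** A dropout rate is normally a share of the participants who enter the trial. The plan applies 20% to the number it wants to finish with, which gives too small an addition. The ten extra subjects are there to offset dropout, yet at the stated rate they do not offset all of it: 60 enrolled does not yield the 50 on which the power statement rests. The sample size statement for the primary outcome is therefore inconsistent with its own assumptions. At stake is an accurate account of the dropout the trial can absorb and of its power at that dropout. The conduct and analysis of the trial are not affected.

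**Working it through.** **Inputs**, all from Sample calculation: 50 required; 20% dropout; 10 added; 60 enrolled, 30 per arm; power 0.80; alpha 0.05.

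**1. Reproduce the plan's figure.** Required × (1 + dropout) = 50 × 1.20 = 60. This matches exactly, so the 20% was applied to the required number.

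**2. Completers at the stated dropout.** Enrolled × (1 − dropout) = 60 × 0.80 = 48, or 24 per arm. Shortfall: 50 − 48 = 2.

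**3. Dropout that 60 does cover.** (60 − 50)/60 = 10/60 = 16.7%.

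**4. Enrolment that would hold 50 at 20%.** Required/(1 − dropout) = 50/0.80 = 62.5, so 63 (63 × 0.80 = 50.4 expected completers). For equal arms, 64 (64 × 0.80 = 51.2).

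**5. Cost in power.** The plan names neither test nor sidedness, so three readings were tried. In each, the effect was set so that 50 subjects give exactly 80% power at alpha 0.05, and power was then recalculated at 48.

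| Assumed test | Power at 50 | Power at 48 | Loss (points) |
|---|---|---|---|
| Two-sample t-test, two-sided (d solved as 0.809) | 80.0% | 78.3% | 1.7 |
| Two-sample t-test, one-sided (d solved as 0.713) | 80.0% | 78.5% | 1.5 |
| Group × Time F-test, five time points, sphericity assumed | 80.0% | 78.1% | 1.9 |

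The F-test has 4 and 4(N − 2) degrees of freedom and a noncentrality parameter proportional to N. The solved values of d serve only to place 80% at N = 50; they are not the plan's effect size.

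**6. Bounds.** The figures at 48 treat every dropout as contributing nothing. With complete data on all 60, the same three settings give 86.9%, 86.1% and 87.6%. With 20% dropout and some information recovered from partial data, power would lie between the two sets.

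**The case against.** Four points can be made for the plan.

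- **The denominator is not stated.** The text does not say what the 20% is a share of, nor that 50 must complete. Read as ten losses against the 50 required, the sentence is consistent with itself. That softens the criticism, but it departs from the usual meaning of dropout, and the plan never says it is using another one.
- **Completers are not the analysis set.** Intention-to-treat with multiple imputation would keep all 60, and a participant lost after week 4 or week 7 has already given TUG data. This stands: 48 is a count of completers, and about 78% is a floor. But the SAP says only that the method will be considered, and imputation does not in general restore all the missing information. The ten subjects were added specifically for dropout, so the plan itself treats dropout as a loss to be offset.
- **The power figures lean on the base of 50.** This also stands. If 0.51 is read as Cohen's d for a two-sample t-test, 50 subjects give 42% power two-sided or 55% one-sided, not 80%. The 78% is therefore conditional on the plan's own claim and is not an estimate of the trial's actual power. How the 50 was obtained is a separate matter; the count of 48 against 50 does not depend on it.
- **The effect is too small to matter.** The effect is small, at one participant per arm. That argues for a light correction, not for leaving the statement inconsistent.

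**Conclusion.** The concern holds, with a minor effect. As written, 60 enrolled does not deliver 50 completers at 20% dropout: it delivers 48, and the dropout it covers is 16.7%. This rests only on dropout being a share of those enrolled. If 50 gives 80% power, the loss at 48 is 1.5 to 1.9 points across the three tests assumed, with no credit for partial data or imputation.

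**What to change.** Keep 60 and restate the dropout step, for example: *With 60 enrolled, 50 complete if dropout is no more than 16.7%; at 20% dropout, 48 (24 per arm) complete.* Add the power at 48 from the G*Power test and inputs that produced the 50. Name that test and its sidedness and, if it was a repeated measures test, give the number of measurements and the assumed correlation, because the restated power cannot be checked without them.

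The cost is one or two sentences, one re-run of an existing calculation and a slightly less favourable stated figure. If the sponsor prefers to hold 50 completers at 20% dropout, enrolling 64 (32 per arm) does so in expectation, at the cost of four more participants. The size of the loss does not require this.
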